7.2. MULTICENTER STUDIES

All centers are to be pooled by treatment group for analysis purposes and no by-center analyses are to be performed.

7.3. MISSING DATA

Missing data will not be imputed. Missing or incomplete dates will not be imputed if not indicated otherwise.

Unless otherwise specified, all analysis will be based on the number of observations in the relative analysis set, i.e. participants with missing information will be included in the denominator when calculating percentages.

7.3.1 MISSING OR PARTIAL ADVERSE EVENT DATES

Missing dates will not be imputed.

7.4. EXAMINATION OF SUBGROUPS

No subgroup analyses will be performed for this study.

8. OUTPUT PRESENTATIONS

APPENDIX 1 shows conventions for presentation of data in outputs.

The templates provided with this SAP describe the presentations for this study and therefore the format and content of the summary tables and listings to be provided by IQVIA Biostatistics.

9. DISPOSITION AND PROTOCOL DEVIATIONS

All participants who provide informed consent will be accounted for in this study.

9.1. DISPOSITION

Participant disposition will be tabulated for each treatment group and for all participants in the following categories:

- Total number of participants Screened (Overall summary only)
- Number of screen failures (Overall summary only)

Document: \$506df00529e1\$BDE32479744D47F0B3BAA4285D5BE091.docx

Author: ████████████████████

Version Number: Final v1.1

Version Date: 16Nov2022

Template No.: CS_TP_BS016 Revision 6

Reference: CS_WI_BS005

Effective Date: 02Dec2019

- o Screen failures reason
 - Number of participants enrolled but not randomised (Overall summary only)
 - Number of participants replaced (Overall summary only)
 - Number of participants randomised
 - o Number and percentage of participants started study drug
 - o Number and percentage of participants did not start study drug
 - Number and percentage of participants on-treatment (DSMB only)
 - Number and percentage of participants off-treatment (DSMB only)
 - Number and percentage of participants completing treatment
 - Number and percentage of participants with study drug discontinuation
 - o Primary reason for treatment discontinuation
 - Number and percentage of participants completed study
 - Number and percentage of participants with study discontinuation
 - o Primary reason for study discontinuation

Percentages for the reasons for failed screening are based on the number of participants who failed screening; percentages for the reasons for study discontinuation are based on the number of participants who prematurely discontinued from the study; all other percentage are based on the number of randomised participants.

The number and percentage of participants included in each analysis set (definitions provided in Section 5) will also be summarized by treatment group and for all participants using frequency tabulations, based on the number of randomized participants.

Listings of study disposition, analysis set assignments, study eligibility, and study drug administration will be provided.

9.2. PROTOCOL DEVIATIONS

A protocol deviation is any noncompliance with the clinical trial protocol, Good Clinical Practice (GCP), or Manual of Procedure requirements. The noncompliance may be either on the part of the participant, the site principal investigator (PI), or the study site staff. Any participant enrolled who does not meet eligibility criteria will be considered an enrolment deviation.

Protocol deviations will be summarized by severity classification (critical, major or minor) and deviation type by treatment group and for all participants.

Protocol deviations will be listed including a severity classification of critical, minor or major, as determined by clinical staff. All participants whose study participation was impacted by COVID-19 will be flagged.

Document: \$506df00529e1\$BDE32479744D47F0B3BAA4285D5BE091.docx

Author: [REDACTED]

Version Number: Final v1.1

Version Date: 16Nov2022

Template No.: CS_TP_BS016 Revision 6

Reference: CS_WI_BS005

Effective Date: 02Dec2019

Copyright © 2009, 2010, 2012, 2016, 2018, 2019 IQVIA. All rights reserved. The contents of this document are confidential and proprietary to IQVIA Holdings Inc. and its subsidiaries. Unauthorized use, disclosure or reproduction is strictly prohibited.

10. DEMOGRAPHIC AND OTHER BASELINE CHARACTERISTICS

Demographic data and other baseline characteristics will be presented for the ITT Analysis Set. Individual participant demographics and baseline characteristics will be presented in listings.

Demographic and baseline characteristics (age, sex, of childbearing potential, race, ethnicity, mRSS at Screening and scleroderma signs and symptoms, FVC, CRISS score, SHAQ-DI, SCTC-DI, 5-D Itch Scale, Patient Global Assessment, Physician Global Assessment) will be summarised and tabulated by treatment group and for all participants.

11. MEDICAL HISTORY/CURRENT MEDICAL CONDITION

Medical history or current medical condition will be presented for the Safety Analysis Set.

Medical history and current medical condition will be coded using Medical Dictionary for Regulatory Activities (MedDRA) central coding dictionary, Version 23.0 or higher. Medical history conditions are defined as those conditions which stop prior to first study drug administration. The number and percentage of participants for each system organ class (SOC) and preferred term (PT) will be summarized by treatment group and for all participants.

Summaries will be presented by SOC and PT, sorted by decreasing overall frequency. In cases of SOC classes or PTs with equal frequencies, it will be sorted alphabetically. Participants will be counted only once for each SOC or PT in the event that they have multiple records of the same SOC or PT term in the database. Medical history will be listed per treatment group.

12. PRIOR AND CONCOMITANT MEDICATIONS

Prior and concomitant medications will be coded using the World Health Organization (WHO) Drug Global Version 01MAR2021 (or later). Prior medications will be recorded up to 1 month prior to baseline observations.

Medications will be grouped by Anatomical Therapeutic Chemical (ATC) system (Level 2) and drug preferred term and summarized by treatment group for the Safety Analysis Set.

- Prior medications are those medications which stopped prior to the first study drug administration.
- Concomitant medications are medications which were taken at least once after the first study drug administration:
 - o started prior to, on or after the first study drug administration AND ended on or after the date of first study drug administration or were ongoing at the end of the study.
 - o Started on or after the date of first study drug administration.

Document: \$506df00529e1\$BDE32479744D47F0B3BAA4285D5BE091.docx

Author: ████████████████████

Version Number:

Final v1.1

Version Date:

16Nov2022

Template No.: CS_TP_BS016 Revision 6

Reference: CS_WI_BS005

Effective Date: 02Dec2019

Copyright © 2009, 2010, 2012, 2016, 2018, 2019 IQVIA. All rights reserved. The contents of this document are confidential and proprietary to IQVIA Holdings Inc. and its subsidiaries. Unauthorized use, disclosure or reproduction is strictly prohibited.

In the listings, each medication will be identified as a prior medication (P), a concomitant medication that started prior to first study drug administration and continued after the first dose of study drug (PC) or a concomitant medication that started after the first dose of study drug ©.

In the summary tables, prior and concomitant medications will be presented by decreasing frequency of total medications overall within each ATC class and then similarly by decreasing frequency of total medications overall within each preferred term. In cases of ATC classes or preferred terms with equal frequencies, medications will be sorted alphabetically.

Systemic Sclerosis Related Concomitant Medications will be summarised separately. Systemic sclerosis (immunosuppressive medications) related concomitant medications will also be summarized separately for participants who have an mRSS increase of 5 or more.

13. STUDY DRUG EXPOSURE AND COMPLIANCE

Participants will be instructed to take two (2) capsules once per day during the treatment period.

Exposure to study drug will be presented for the Safety Analysis Set. A data listing containing the study drug administration details will be provided.

The date of first and last study drug administration will be taken from the drug administration eCRF form. Interruptions and compliance are not taken into account for duration of exposure.

Duration of exposure will be summarized by treatment group and for all participants.

13.1. DERIVATION

Duration of exposure (weeks) = (date of last study drug administration – date of first study drug administration + 1) / 7

13.2. STUDY DRUG COMPLIANCE

Compliance to the study drug will be presented for the ITT Analysis Set.

Overall treatment compliance will be summarized by treatment group and for all participants.

Kit dispensed, kit return details and study drug compliance will be listed per treatment group.

13.3. DERIVATION

$$Compliance (\%) = \frac{\text{number of capsules taken}}{(\text{date of kit returned} - \text{date of kit dispensed} + 1) \times 2} \times 100$$

Overall study drug compliance will be calculated as:

$$Overall\ Treatment\ Compliance = [1 - (\frac{\text{total number number of days of study drug interruption}}{\text{Duration of study drug exposure in days}})] \times$$

Document: \$506df00529e1\$BDE32479744D47F0B3BAA4285D5BE091.docx

Author: [REDACTED]

Version Number: Final v1.1

Version Date: 16Nov2022

Template No.: CS_TP_BS016 Revision 6

Reference: CS_WI_BS005

Effective Date: 02Dec2019

100,

Where duration of study drug exposure is derived as date/time of last treatment – date/time of first treatment + 1.

14. PHARMACOKINETIC, EFFICACY AND PHARMACODYNAMIC ANALYSIS

14.1. PHARMACOKINETIC ANALYSIS

Pharmacokinetic data collected and analysed will be presented as described in this section. All PK analysis will be presented using the PK Analysis set.

14.1.1 PHARMACOKINETIC SAMPLE COLLECTION

Blood samples for plasma PK analyses will be collected at the following time points:

- Day 1: within 30 minutes prior to IMP administration, and at 1, 2, 3, 4, 5, 6, 7 and 8 hours post dose.
- Week 4: within 30 minutes prior to IMP administration.
- Week 8: within 30 minutes prior to IMP administration.
- Week 12: within 30 minutes prior to IMP administration, and at 1, 2, 3, 4, 5, 6, 7 and 8 hours post dose.

A window of ± 10 minutes is allowed for all time points. Collections outside of these windows will be recorded as protocol deviations. Actual collection time must be recorded. At each visit, the time of administration of the previous dose of IMP, and the time the dose is taken at the study site, must be recorded.

14.1.2 PHARMACOKINETIC CONCENTRATIONS

Plasma FT011 (and any metabolite) concentrations data will be summarised by visit and nominal collection time points using descriptive statistics including the number of concentrations below the limit of quantification (BLQ), CV%, geometric mean, and geometric CV%.

Results reported as BLQ will be treated as zero for the calculation of the summary statistics, and as missing for the calculation of the geometric statistics.

Spaghetti plots of the individual plasma FT011 concentrations vs. actual time profiles (relative to the dose at the visit) will be presented on linear and log-linear scales. Plots will be presented by treatment group and visit. BLQ concentrations will be set to 0 in the linear plots and will be treated as half of lower limit of quantification ($0.5 \times \text{LLOQ}$) in the log-linear plots.

Mean concentration profiles (\pm SD bars) vs. nominal time curves will be presented by visit on linear and log-linear scales.

Document: \$506df00529e1\$BDE32479744D47F0B3BAA4285D5BE091.docx

Author: [REDACTED]

Version Number:

Final v1.1

Version Date:

16Nov2022

Template No.: CS_TP_BS016 Revision 6

Reference: CS_WI_BS005

Effective Date: 02Dec2019

Copyright © 2009, 2010, 2012, 2016, 2018, 2019 IQVIA. All rights reserved. The contents of this document are confidential and proprietary to IQVIA Holdings Inc. and its subsidiaries. Unauthorized use, disclosure or reproduction is strictly prohibited.

All plasma FT011 concentration data will be listed, and the listing will include the calculated elapsed time since the study drug administration at the specific visit and the time deviations between the actual and planned sample collection times.

14.1.3 PHARMACOKINETIC PARAMETERS

Two sets of plasma FT011 PK parameters will be calculated based on the concentrations collected after the single dose on Day 1 and based on the concentrations collected after the last dose at Week 12. Plasma PK parameters will be calculated using a non-compartmental approach (Phoenix WinNonlin version 8.3 or higher) based on the observed concentration-time profiles. Actual sampling times relative to the dose at the visit will be used in all PK calculations. The PK set will be used for the pharmacokinetic parameter calculations. The following PK parameters will be determined for FT011 and additional parameters may be added at the discretion of the pharmacokineticist.

PK Parameter	Method
C _{max}	Maximum observed concentration
t _{max}	Time to reach maximum concentration
AUC ₀₋₈	Area under the plasma concentration-time curve from the time of the dose administration to the time of the 8-hour post-dose concentration calculated by the linear up log down trapezoidal method
AUC _{last}	Area under the concentration-time curve from the time of the dose administration to the time of the last measurable concentration calculated by the linear up log down trapezoidal method

All predose BLQ values will be substituted by zeros. Thereafter BLQ values will be set as “missing”.

The plasma PK parameter results will be summarised by treatment group and visit using summary statistics and the geometric statistics described for the PK concentrations. All plasma PK parameter results will be listed.

Results will also be presented graphically using box-and-whisker plots.

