## **7 TRIAL ENDPOINTS**

### **7.1 Primary Endpoints**

- FT011  $c_{max}$ ,  $t_{max}$ , and AUC in plasma after a single dose and after 12-weeks of treatment.
- Measurement of steady state FT011 levels in plasma.

Additional calculations may be performed, and metabolites may also be measured.

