### 12.4.3.2 Pharmacokinetic Parameters

Two sets of plasma FT011 PK parameters will be calculated based the concentrations collected after the single dose on Day 1 and based on the concentrations collected after the last dose at Week 12.

Plasma PK parameters will be calculated using a non-compartmental approach based on the observed concentration-time profiles. Actual sampling times relative to the dose at the visit will be used in all PK calculations. The handling of BLQ values in the parameter calculations will be described in the SAP.

The plasma PK parameters shown in Table 3 will be calculated (data permitting) from the concentration-time profiles and additional parameters may be added at the discretion of the pharmacokineticist

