2. STUDY OBJECTIVES AND ENDPOINTS

2.1. PRIMARY OBJECTIVE AND ENDPOINTS

The primary objective is:

- To assess the PK of oral FT011 in participants with diffuse systemic sclerosis (SSc)

The primary endpoints are:

- FT011 (Maximum plasma concentration (C_{max}), Time to maximum concentration (t_{max}), and Areas under the Curve (AUC) in plasma after a single dose and after 12-weeks of treatment.
- Measurement of steady state FT011 levels in plasma.

Note: additional calculations may be performed, and metabolites may also be measured.

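### Setting leading post-dose BLQ values to missing inflates AUC0-8 and AUClast in any profile where the first sample or samples after dosing are BLQ; how often that happens cannot be told from the documents

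*SAP*

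**What the plan says.** AUC is a primary endpoint at both PK visits. Protocol 7.1 lists "AUC in plasma after a single dose and after 12-weeks of treatment", and SAP 2.1 repeats it.

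Protocol 12.4.3.2 leaves the BLQ rule to the SAP: "The handling of BLQ values in the parameter calculations will be described in the SAP". The rule in SAP 14.1.3 is: "All predose BLQ values will be substituted by zeros. Thereafter BLQ values will be set as" missing. It does not separate a BLQ value before the first quantifiable concentration from one that follows it.

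The same section defines AUC0-8 as running "from the time of the dose administration to the time of the 8-hour post-dose concentration", and both AUC0-8 and AUClast are "calculated by the linear up log down trapezoidal method". The sampling grid in SAP 14.1.1 is "Day 1: within 30 minutes prior to IMP administration, and at 1, 2, 3, 4, 5, 6, 7 and 8 hours post dose", with the same times at Week 12.

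SAP 14.1.2 does score BLQ as zero, but only for arithmetic summaries of concentrations and for linear plots. It does not reach the AUC calculation.

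**The concern.** A BLQ result at 1 h is information: the concentration then was below the assay limit. Deleting it puts an interpolated value in its place. With one leading BLQ sample and a first quantifiable value C at 2 h, the straight line from zero implies C/2 at 1 h. Whenever C is more than twice the LLOQ, that implied value is above the limit the assay says was not reached.

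Deleting BLQ values is a common choice once the drug has been quantified and is falling. On the rising side it adds area, and in most cases the area is spurious. The resulting error in an affected profile is mostly upward, so averaging over participants does not remove it.

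At stake is the accuracy of individual AUC values, and through them the group geometric mean and CV, for a primary endpoint with about 10 participants per arm. Delayed absorption is possible in this population: Protocol 5.4.3 excludes gastrointestinal dysmotility only when it needs total parenteral nutrition or has led to hospitalisation in the previous 6 months.

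**Working it through.** The plan states no figure for this point, so there is none to reproduce.

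**Inputs from the documents**
- Pre-dose BLQ = 0; every later BLQ = missing (SAP 14.1.3).
- Linear-up/log-down trapezoid starting at dosing (SAP 14.1.3).
- Samples at 0, 1, 2, …, 8 h (SAP 14.1.1; nominal times used here).
- About 10 participants per group (Protocol 12.1).

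**Inputs assumed, because the documents give none**
- One-compartment oral kinetics, half-life 2–8 h, absorption rate ka 0.7–1.5/h, absorption lag 1–2 h.

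**Step 1: the algebra (no kinetic assumption).** Let the pre-dose sample be BLQ, the samples at 1 to k h be BLQ, and the first quantifiable value be C at k+1 h. A rise is integrated linearly.
- SAP rule: area up to k+1 h = 0.5 × (k+1) × C.
- Leading BLQ set to zero: area up to k+1 h = 0.5 × 1 × C.
- Difference = 0.5 × k × C, identical for AUC0-8 and AUClast.

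Example: 1 h BLQ and 2 h = 60 gives 0.5 × 2 × 60 = 60 against 0.5 × 1 × 60 = 30.

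**Step 2: a whole profile.** First quantifiable value 60, next value 100, then a 20% fall each hour to 8 h.

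| Leading BLQ samples (k) | AUC0-8, SAP rule | AUC0-8, leading zeros | Difference |
|---|---|---|---|
| 1 | 441.3 | 411.3 | 30 (+7.3%) |
| 2 | 434.6 | 374.6 | 60 (+16.0%) |
| 3 | 418.7 | 328.7 | 90 (+27.4%) |

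The differences equal 0.5 × k × 60, as Step 1 requires. They compare two rules and are not bias against the truth.

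**Step 3: against the true area.** With x = t − lag, the concentration is proportional to ka/(ka − ke) × [exp(−ke·x) − exp(−ka·x)] for x > 0 and is zero before that, with ke = ln 2 / half-life. The true AUC0-8 is the exact integral. Ranges are over the assumed half-lives and ka.

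| Lag | Leading BLQ samples | SAP rule / true | Leading zeros / true |
|---|---|---|---|
| 1 h | 1 | 1.04–1.07 | 0.95–0.99 |
| 1.25–1.75 h | 1 | 1.02–1.11 | 0.99–1.02 |
| 2 h | 2 | 1.11–1.20 | 0.94–0.98 |

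Faster kinetics widen both errors. With ka 0.5–2/h, ke 0.1–0.7/h, an LLOQ of 1% of dose/volume and lags up to 2.5 h, the SAP rule runs from about 0% to +22% with one leading BLQ sample and from +8% to +41% with two. Leading zeros run from about −13% to +3%.

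**Step 4: the reported summary.** If m of 10 participants have AUC inflated by a factor r, the group geometric mean is multiplied by r^(m/10).
- One at +7%: 1.07^0.1 = 1.007.
- One at +20%: 1.20^0.1 = 1.018.
- Two at +20%: 1.20^0.2 = 1.037.

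**Step 5: Week 12.** With ka 1/h and lags of 1.5 and 2.5 h at steady state:
- ke 0.05–0.1/h: the trough is quantifiable, no post-dose sample is BLQ, and the rule changes nothing.
- ke 0.3–0.7/h: the trough is BLQ and AUC0-8 is overstated by 8–26%, as on Day 1.

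**The case against.** **The trigger may never occur.** The effect needs at least the 1 h sample to be BLQ. Dosing is on an empty stomach, the most severe dysmotility is excluded, and the public documents give no LLOQ, lag or half-life (the PK background is blacked out, which is no fault of the plan). If every 1 h sample is quantifiable, nothing changes. This stands: frequency is unknown, and the two-sample case needs a further step that the documents do not support.

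**The replacement rule is not exact.** BLQ means below the limit, not zero. At a 1 h lag, leading zeros are 1–5% low where the SAP rule is 4–7% high. Outside the main range the SAP rule can be the closer one. With ka 2/h, ke 0.7/h and absorption starting just before 1 h, it is 6.8% high while leading zeros are 12.9% low. When absorption starts just before the first quantifiable sample, the SAP rule is almost exact. Across the main assumed range in Step 3, however, leading zeros are closer to the truth.

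**The consequence is limited.** PK is summarised descriptively, with no test or AUC threshold. BLQ counts are tabulated and all concentrations are listed, so an affected AUC could be found and recomputed. This also stands, and it limits the priority of the point.

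**A stronger reading.** A reader might infer that the rule distorts Day 1 against Week 12 and so understates accumulation. That needs delayed absorption on Day 1 together with a quantifiable Week 12 trough. Neither is documented, and neither document specifies an accumulation ratio or a comparison of the two visits. If the Week 12 pre-dose sample is BLQ, Week 12 is inflated in the same way.

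**Conclusion.** The point holds in conditional form. As written, the rule adds exactly 0.5 × k × C to AUC0-8 and AUClast, relative to leading zeros, in any profile with a BLQ pre-dose sample and k leading BLQ samples on the hourly grid. That follows from the SAP text alone, and nothing elsewhere overrides it.

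The size against the truth rests on assumed kinetics (one compartment, half-life 2–8 h, ka 0.7–1.5/h): about 2–11% too high with one leading BLQ sample and 11–20% with two, for the affected participant. At group level this is about 1–4% on the geometric mean if one or two of ten are affected, and nothing if none are.

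The documents do not support saying that the reported primary AUC will be biased, because they do not show that leading BLQ samples will occur. Nor do they support extending the point to Cmax or tmax, which do not depend on this rule. It is a stated rule that gives a worse answer than an equally simple alternative over the main assumed range, and it is worth correcting because correction is nearly free.

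**What to change.** Replace the rule in SAP 14.1.3 with wording to this effect: for AUC calculation, pre-dose BLQ values and BLQ values before the first quantifiable post-dose concentration are set to zero; BLQ values after the first quantifiable concentration are set to missing.

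The cost is one SAP sentence and one setting in the PK software. No new data or procedures are needed, and no AUC changes if no leading BLQ sample occurs. The downside is that AUC may be slightly understated when absorption begins close to the last BLQ sample: by about 1–5% with one leading sample (1 h lag) and 2–6% with two (2 h lag) under the main assumptions.
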